5.1.1 Additional Analysis of the Primary Efficacy Outcome Measure

In addition to the primary efficacy outcome measure, following sensitivity analyses will be performed on Day 12 (+/- 1 day) in the m-MITT population,

- Sensitivity Analysis 1: Will follow the same definition of primary outcome measure defined in section 5.1 except, urgency is excluded and considering all other symptoms (in Appendix 2) are resolved and no new uUTI symptoms.
- Sensitivity Analysis 2: Will follow the same definition of primary outcome measure defined in section 5.1 except, frequency is excluded and considering all other symptoms (in Appendix 2) are resolved and no new uUTI symptoms.
- Sensitivity Analysis 3: Will follow the same definition of primary outcome measure defined in section 5.1 except, improvement of symptoms (instead of resolution, in Appendix 2) from baseline and no worse than mild from baseline and no new uUTI symptoms are considered.
- Sensitivity Analysis 4: Will follow the same definition of primary outcome measure defined in section 5.1 except, improvement of symptoms (instead of resolution, in Appendix 2) from baseline and no new uUTI symptoms are considered.
- Sensitivity Analysis 5: Will follow the same definition of primary outcome measure defined in section 5.1 except, urgency and frequency are improved and no worse than mild from baseline and all other symptoms (in Appendix 2) are resolved and no new uUTI symptoms are considered.
- Sensitivity Analysis 6: Will follow the same definition of primary outcome measure defined in section 5.1 except, investigator response will be used instead of symptoms filled in by patient (from patient dairy).

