Microbiologic response assessments will be made based on quantitative cultures performed on collected urine specimens.

Statistical Methods:

General Statistical Considerations:

Descriptive statistics, including the numbers and percentages for categorical variables, and the numbers, means, standard deviations, medians, minimums, and maximums for continuous variables will be provided. Comparisons will be made between response rates for patients with infection due to ciprofloxacin-susceptible and ciprofloxacin-non-susceptible isolates. Exploratory analyses may also be performed. Listings of individual patient's data will be produced.

Efficacy Analyses:

The study is designed to determine the clinical and microbiologic response of patients with a uUTI, due to ciprofloxacin-sensitive and ciprofloxacin-non-susceptible isolates, treated with ciprofloxacin for the outcome measure of overall response (combined clinical and microbiologic response) at Day 12 (+/- 1 day).

A patient will be defined as a responder if the following criteria are met:

- The patient is alive
- The patient has received no rescue therapy for uUTI
 - If an antibiotic active against the urinary tract pathogen is given for other reasons, then the patient will be considered indeterminate, and analyzed as a non-responder for uUTI
- The patient has resolution of the symptoms of uUTI present at trial entry and no new uUTI symptoms
- Urine culture taken on Day 12 (+/- 1 day) demonstrates <10³ CFU/mL of the baseline uropathogen

All other patients will be considered non-responders. If data are unavailable to determine if the patient is a responder or non-responder, the patient will be considered an indeterminate response.

The number and percentage of responders, non-responders and indeterminates will be determined. Descriptive statistics, including the numbers and percentages for categorical variables, and the numbers, means, standard deviations, medians, minimums, and maximums for continuous variables will be provided. In addition to the randomized m-MITT population, additional analyses will be performed in the subset of patients with ciprofloxacin-susceptible organisms at baseline and in

Clinical Trial Protocol: IT-004-401

those with ciprofloxacin-non-susceptible organisms at baseline. Exploratory analyses may also be performed. Listings of individual patient's data will be produced. A comprehensive Statistical Analysis Plan (SAP) will be finalized prior to the database lock.

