producing organisms include nitrofurantoin, fosfomycin, fluoroquinolones and trimethoprim-sulfamethoxazole. Nitrofurantoin and fosfomycin are only approved for the treatment of uncomplicated urinary tract infections in the United States, have rising rates of resistance and are associated with inferior efficacy [Munoz-Davila 2014; Schito 2009]. Resistance to trimethoprim-sulfamethoxazole is uniformly above 20% in the US. Increasing prevalence of resistance to fluoroquinolones and their propensity to cause collateral damage resulted in relegation of fluoroquinolones to second-line therapy by the Infectious Disease Society of America (IDSA) for UTI [Gupta 2011]. Even with these limitations, almost two-thirds of patients with a uUTI receive therapy with a fluoroquinolone antibiotic. Furthermore, there is a percentage of uUTI patients treated with a fluoroquinolone who respond to therapy despite predicted failure based upon the results of in vitro susceptibility testing. The reason for this is likely multifactorial, including PK/PD relationships (i.e., concentration and duration of drug at the site of infection) and host factors. The proportion of patients with infection due to fluoroquinolone resistant pathogens who have clinical or bacteriological response to fluoroquinolone therapy has not been well studied, and most studies which have evaluated this issue have done so as part of a secondary analysis of a UTI treatment trial.

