9.3 General Statistical Considerations

Descriptive statistics, including the numbers and percentages for categorical variables, and the numbers, means, standard deviations, medians, minimums, and maximums for continuous variables will be provided. Comparisons will be made between response rates for patients with infection due to ciprofloxacin-susceptible and ciprofloxacin-non-susceptible isolates. Exploratory analyses may also be performed. Listings of individual patient's data will be produced. A comprehensive Statistical Analysis Plan (SAP) will be finalized prior to final database lock.

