9.5.1.1 Additional Analyses of the Primary Efficacy Outcome

In addition to the overall response rate, response rates for patients infected by ciprofloxacin susceptible and non-susceptible organism will be evaluated.

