1 INTRODUCTION

This document presents the Statistical Analysis Plan (SAP) for the IT-004-401, "A prospective, Phase 4 open label, multi-center study of the clinical and microbiologic efficacy of ciprofloxacin for the treatment of uncomplicated urinary tract infections in adult women." This plan contains definitions of analysis populations, derived variables and statistical methods for the analysis of clinical and microbiologic efficacy. The statistical plan described is an "a priori" plan, and the analyses outlined here have not been conducted prior to the preparation of this plan.

This SAP summarizes the design and objectives of protocol IT-004-401 and provides details of the definitions of the outcome measures and statistical methodology that will be used to analyze the data from the study. Any deviation from the planned analysis will be documented in clinical study report (CSR).

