- Overall response at Day 12 (+/- 1 day) (TOC) in the ITT, CE-TOC and ME-TOC population (m-MITT is used with the primary endpoint)
- Overall response, microbiologic response, clinical response and investigator response at the EOT and TOC visits by baseline pathogen (key pathogens) in the m-MITT and ME populations
- Overall response, microbiologic response and clinical response at the EOT and TOC visits by baseline ESBL in the m-MITT and ME populations
- Distribution of pathogens by culture concentration at EOT and TOC in the m-MITT, ME-EOT and ME-TOC populations

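### The SAP's efficacy sections leave out the response rates by ciprofloxacin susceptibility, and their comparison, that the protocol promises, and SAP Section 8 does not record the change

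*SAP*

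**What the plan says.** **Protocol.** The synopsis describes a study of patients with infection "due to ciprofloxacin-sensitive and ciprofloxacin-non-susceptible isolates, treated with ciprofloxacin for the outcome measure of overall response" at Day 12, and states that "additional analyses will be performed in the subset of patients with ciprofloxacin-susceptible organisms at baseline" and in the non-susceptible subset. Section 9.3 says "Comparisons will be made between response rates for patients with infection due to ciprofloxacin-susceptible and ciprofloxacin-non-susceptible isolates". Section 9.5.1.1, on additional analyses of the primary outcome, has one item: "response rates for patients infected by ciprofloxacin susceptible and non-susceptible organism will be evaluated". The rationale in 1.2.1 explains why this matters: the proportion of patients with "infection due to fluoroquinolone resistant pathogens who have clinical or bacteriological response to fluoroquinolone therapy has not been well studied".

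**SAP.** The Introduction says the document "provides details of the definitions of the outcome measures and statistical methodology that will be used to analyze the data from the study". Section 5.1.1, the counterpart of protocol 9.5.1.1, opens "In addition to the primary efficacy outcome measure, following sensitivity analyses will be performed on Day 12 (+/- 1 day" and gives six sensitivity analyses. Section 5.3 breaks response down by baseline pathogen and, separately, has "Overall response, microbiologic response and clinical response at the EOT and TOC visits by baseline ESBL in the m-MITT and ME populations". Section 6.4 derives a final baseline ciprofloxacin susceptibility from central and local laboratory results. Section 7.1 uses that status as columns when counting patients in each population. Section 7.6 specifies descriptive statistics only, on the ground that there is one treatment group. Section 8 lists four topics on which the SAP differs from the protocol: evaluability rules, non-responder rules, Day 21 analyses and the clinical-failure rule.

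**The concern.** The analysis that the protocol attaches to its primary outcome does not appear in any SAP efficacy section, and the section that should hold it contains other analyses. A programmer working from the SAP's efficacy lists would produce a pooled response rate, a by-pathogen table and an ESBL table. None of these gives response by ciprofloxacin susceptibility. ESBL status is set from ceftriaxone in SAP 6.4, so it is not a ciprofloxacin grouping, and one pathogen species can include both susceptible and non-susceptible isolates.

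A second gap follows from the first. Because no susceptibility analysis is written down, no rule says how a patient is classified when two baseline uropathogens differ in susceptibility, or when an isolate has no susceptibility result. If the table is added after the data have been seen, that choice will be made late. SAP 4.7 has the sponsor reviewing clinical and microbiological data while the study runs.

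**Working it through.** **1. Protocol and SAP side by side**

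| Topic | Protocol | SAP |
|---|---|---|
| Additional analyses of the primary outcome | 9.5.1.1: rates by ciprofloxacin susceptibility, nothing else | 5.1.1: five changes to the symptom rule, one use of investigator response |
| Comparison of the two groups | 9.3 and synopsis: promised | 5.1.1, 5.3, 7.6: none, not even descriptive |
| Other splits of response | 9.5.3: by baseline pathogen | 5.3: by baseline pathogen and by ESBL |
| Susceptibility status | synopsis, 9.1, 9.3, 9.5.1.1 | mentioned in 6.1, derived in 6.4, tabulated only in 7.1 (population counts) |
| Declared differences | not applicable | Section 8: this item absent |

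**2. Planned counts.** Protocol 9.1 and SAP 6.1 expect 250 enrolled, 50 without a qualifying culture and 40 with a non-susceptible organism. They give no response rate, power or precision target, so there is no sample-size calculation to reproduce.

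- Culture-positive: 250 − 50 = 200.
- Susceptible: 200 − 40 = 160, if all 40 non-susceptible patients are culture-positive.

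**3. What a pooled rate conceals.** Each row gives the same m-MITT result, 152/200 = 76%. The splits are assumed.

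| Non-susceptible | Susceptible | Difference (points) |
|---|---|---|
| 30/40 = 75.0% | 122/160 = 76.25% | 1.25 |
| 24/40 = 60.0% | 128/160 = 80.0% | 20.0 |
| 16/40 = 40.0% | 136/160 = 85.0% | 45.0 |

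**4. Could the classification rule matter?** Start from 24/40 v 128/160. Suppose k of the 40 have discordant isolates and are counted as susceptible instead, with r of those k responding. The rates become (24 − r)/(40 − k) and (128 + r)/(160 + k).

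| k | r | Non-susceptible | Susceptible | Difference (points) |
|---|---|---|---|---|
| 2 | 2 | 22/38 = 57.9% | 130/162 = 80.2% | 22.4 |
| 2 | 0 | 24/38 = 63.2% | 128/162 = 79.0% | 15.9 |
| 5 | 5 | 19/35 = 54.3% | 133/165 = 80.6% | 26.3 |
| 5 | 0 | 24/35 = 68.6% | 128/165 = 77.6% | 9.0 |

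The documents do not say how often discordance occurs; 2 and 5 are illustrations. Both situations are possible under the plan. The m-MITT admits cultures with two species (SAP 4.4), and SAP 4.5(d) provides for coinfection with a ciprofloxacin-resistant gram-positive uropathogen. Protocol Appendix 2 commits to local susceptibility testing of gram-negative pathogens only, while SAP Appendix 3 admits *S. saprophyticus* to the m-MITT and SAP 6.4 lets a local result be final. The group labelled other in SAP 7.1 is described by absent pathogens and contaminated samples, not by untested isolates.

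**5. Would the table be informative?** 95% intervals, Wilson for a rate and Newcombe for susceptible minus non-susceptible, at assumed rates of 80% and 60%:

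| | Non-susceptible | Susceptible | Difference (points) |
|---|---|---|---|
| 40 v 160 | 24/40: 44.6% to 73.7% | 128/160: 73.1% to 85.5% | 20 (4.7 to 36.3) |
| 20 v 180 (assumed shortfall) | 12/20: 38.7% to 78.1% | 144/180: 73.6% to 85.2% | 20 (0.8 to 42.0) |

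For reference, the pooled 152/200 has a Wilson interval of 69.6% to 81.4%.

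**The case against.** The SAP does not withdraw the protocol's promise. SAP 6.1 keeps the design aim for both organism types, 6.4 derives the status and 7.1 sets up susceptible, non-susceptible, other and total columns for every population. The efficacy tables may have been meant to share that layout, and table shells, which could settle it, are not among the documents. This stands as far as intent goes: the analysis cannot be called abandoned. But 7.1 applies the columns to patient counts, no efficacy section repeats them, and 5.3 names its other splits explicitly.

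Section 8 is incomplete in other respects. It does not mention the six sensitivity analyses, the ESBL split or the organism restriction of the m-MITT in SAP Appendix 3. Silence there therefore says little about this item in particular. That is fair, but the remedy is still either to specify the analysis or to record its removal.

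The primary outcome is the pooled m-MITT rate, the stated primary objective does not mention susceptibility, and the protocol calls the split additional. Patient and isolate listings (SAP 6.6 and 7.3) keep the data available. All of this is correct. It limits the consequence to a missing prespecified analysis and leaves the primary result sound.

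The protocol's comparison need not be a test, and confidence intervals were never promised. Both points are accepted, and side-by-side rates with a descriptive difference would honour the protocol. The response rates, discordance counts and 20-patient scenario above are assumptions. They show what could be hidden and do not predict it.

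**Conclusion.** The concern holds and should be fixed. The protocol promises overall response by ciprofloxacin susceptibility and a comparison, in the synopsis, 9.3 and 9.5.1.1. SAP 5.1.1, 5.3 and 7.6 specify neither, and Section 8 does not declare the difference. The conclusion rests on the texts alone and needs no assumed rate.

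Its practical size depends on assumptions. With 40 and 160 patients, one pooled rate of 76% fits group differences from 1.25 to 45 points, so the pooled result cannot answer the question raised in the rationale. Leaving the classification rule open could move an assumed 20-point difference to between 9.0 and 26.3 points if five patients were discordant, or between 15.9 and 22.4 if two were. The primary m-MITT estimate is unaffected.

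**What to change.** Add to SAP 5.1.1: overall response at test of cure in the m-MITT by baseline ciprofloxacin susceptibility as derived in 6.4, with the susceptible minus non-susceptible difference presented descriptively. ME-TOC can serve as support; clinical and microbiologic response by susceptibility are optional.

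State a patient-level rule:

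- for discordant baseline uropathogens, for example non-susceptible if any of them is;
- for an isolate with no susceptibility result, for example an unknown row kept in the total.

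Date the rule and say whether it was set before susceptibility and outcome were viewed together.

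As an improvement, not a correction of a protocol departure, give Wilson or exact 95% intervals for each group rate and for the primary m-MITT rate, and a Newcombe or Miettinen-Nurminen 95% interval for the difference. This is estimation without a test, so the sentence in 7.6 about a single treatment group can stay.

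If the analysis is left out on purpose, record that and the reason in Section 8.

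The cost is one required table, one supporting table and a few lines of text. No new data are needed, because 6.4 already derives the status. A deliberate omission costs one line. The drawback is that the wide intervals in the non-susceptible group will be visible.

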5.2 Secondary Efficacy Outcome Measure

All symptomatic subjects enrolled in the study will have a positive urine dipstick for both leukocyte esterase and nitrite. The number and percentage of subjects who go on to have a positive baseline urine culture for $\geq 10^5$ CFU/mL of a uropathogen will be evaluated.

5.3 Additional Efficacy Outcomes Measures

Microbiologic response

Microbiologic response is assessed on Day 3 or 4 (+1 day) EOT and Day 12 (+/- 1 day) TOC in the ITT, m-MITT, CE-EOT, CE-TOC, ME-EOT and ME-TOC populations.

Microbiological	Definition
response	
Eradication	A urine culture taken at baseline and compared with the culture
	from the Day 3 (+1 day) (EOT) visit or Day 12 (+/- 1 day)
	(TOC) visit showed that the urine culture obtained at the
	relevant visit demonstrated <10 ³ CFU/mL of the original
	uropathogen.
Persistence	Uropathogen present at baseline grew at ≥10 ³ CFU/mL at the
	time-point of analysis, i.e. EOT or TOC.
Indeterminate	Patient was lost to follow-up or an assessment was not
	undertaken such that no urine culture was obtained (or culture
	results could not be interpreted for any reason) at either the
	EOT or the TOC visit.

• Clinical response:

Clinical response (done programmatically) will use the definitions below to document response at Day 3 or Day 4 (+ 1 day) (EOT), Day 12 (+/- 1 day) (TOC) and Day 21 in the ITT, m-MITT, CE-EOT, CE-TOC, ME-EOT and ME-TOC populations.

Clinical response	Definition
Clinical cure	All pre-therapy signs and symptoms of the index infection had resolved such that no additional antibiotics were required
Clinical failure	Patients who met any one of the criteria below were considered as failure:
	Death related to uUTI prior to Day 3 or Day 12 or Day 21 respectively
	No apparent response to treatment; persistence or progression of most or all pre-therapy signs and symptoms or use of additional antibiotics for the current infection
	Patient previously met criteria for failure and received rescue antibiotics
Indeterminate	Study data were not available for evaluation of efficacy for any reason, including:
	Patient lost to follow-up or assessment not undertaken such that a determination of clinical response could not be made at either the EOT or TOC visit
	Death prior to Day 3 or Day 12 or Day 21, respectively, where uUTI was clearly noncontributory

In addition to the clinical response above, following sensitivity analyses will be performed on Day 12 (+/- 1 day) in the m-MITT population,

- Sensitivity Analysis 1: Will follow the same definition of clinical response defined in section 5.3 except, urgency is excluded and considering all other symptoms are resolved and no new uUTI symptoms.
- Sensitivity Analysis 2: Will follow the same definition of clinical response defined in section 5.3 except, frequency is excluded and considering all other symptoms are resolved and no new uUTI symptoms.
- Sensitivity Analysis 3: Will follow the same definition of clinical response defined in section 5.3 except, improvement of symptoms (instead of resolution) from baseline and no worse than mild from baseline and no new uUTI symptoms are considered.
- Sensitivity Analysis 4: Will follow the same definition of clinical response defined in section 5.3 except, improvement of symptoms (instead of resolution) from baseline and no new uUTI symptoms are considered.
- Sensitivity Analysis 5: Will follow the same definition of clinical response defined in section 5.3 except, urgency and frequency are improved and no worse than mild from baseline and all other symptoms are resolved and no new uUTI symptoms are considered.

• Investigator response:

Investigator-determined response will use the definitions below to document response at Day 3 or Day 4 (+ 1 day) (EOT) and Day 12 (+/- 1 day) (TOC) in the ITT, m-MITT, CE-EOT, CE-TOC, ME-EOT and ME-TOC populations.

Clinical response	Definition			
Clinical cure	All pre-therapy signs and symptoms of the index infection had resolved such that no additional antibiotics were required			
Clinical failure	Patients who met any one of the criteria below were considered as failure:			
	Death related to uUTI prior to Day 3 or Day 12, respectively			
	No apparent response to treatment; persistence or progression of most or all pre-therapy signs and symptoms or use of additional antibiotics for the current infection			
	Patient previously met criteria for failure			

Clinical response	Definition
Indeterminate	Study data were not available for evaluation of efficacy for any reason, including:
	Patient lost to follow-up or assessment not undertaken such that a determination of clinical response could not be made at either the EOT or TOC visit
	Death prior to Day 3 or Day 12, respectively, where uUTI was clearly noncontributory

- Patient Symptom Assessment Questionnaire (filled out by patient) at Day 3 or Day 4 (+ 1 day) (EOT) and Day 12 (+/- 1 day) (TOC) in the ITT, m-MITT, CE-EOT, CE-TOC, ME-EOT and ME-TOC populations
- Overall response at Day 3 or Day 4 (+ 1 day) (EOT) in the ITT, m-MITT, CE-EOT and ME-EOT populations
- Overall response at Day 12 (+/- 1 day) (TOC) in the ITT, CE-TOC and ME-TOC population (m-MITT is used with the primary endpoint)
- Overall response, microbiologic response, clinical response and investigator response at the EOT and TOC visits by baseline pathogen (key pathogens) in the m-MITT and ME populations
- Overall response, microbiologic response and clinical response at the EOT and TOC visits by baseline ESBL in the m-MITT and ME populations
- Distribution of pathogens by culture concentration at EOT and TOC in the m-MITT, ME-EOT and ME-TOC populations

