5.4 Medication(s), Adjunctive Therapy and Non-drug Therapy

5.4.1 Concomitant Medications

Any medication taken by the patient, other than ciprofloxacin, is considered a concomitant medication. Any concomitant medication which is administered from Screening through the TOC Visit must be recorded in the patient's source record.

Any concomitant medication which is an antibiotic, administered for the treatment of the primary uUTI, should also be recorded in the CRF. No other concomitant medications need to be recorded in the CRF.

At each visit, the Investigator or site designee will obtain information on any therapeutic interventions (e.g., drug and non-drug therapy, surgery, etc.) provided. The use of any investigational drug is prohibited and patients may not participate in any other studies involving other marketed products concomitantly while in this study.

The use of other (non-antibacterial) medications should be limited to those essential for the care of the patient. All medications required by the patient to manage underlying illnesses, other than the infection under study, and any drugs that may be required for emergency treatments must be recorded in the source document.

The bioavailability of ciprofloxacin is significantly reduced when co-administered with magnesium or aluminum containing antacids. As a result, co-administration of these antacids with ciprofloxacin is not permitted.

Dosing with food does not affect the overall absorption of ciprofloxacin.

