6.3.2 Post Test of Cure (TOC) Day 21 (+/- 3 days)

Call patient to assess for resolution of uUTI symptoms

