13 DEFINITION OF END OF STUDY

13.1 End of Study in Participating Countries

End of Study in all participating countries is defined as the TOC Visit.

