8 DIFFERENCES WITH ANALYSES SPECIFIED IN THE PROTOCOL

- The clinical evaluability rules in the protocol have been modified in the SAP (section 4.5). The prior antibiotic rule was dropped because it is an exclusion criterion in the protocol and applicable to all patients. The requirement that a study entry urine culture obtained before ciprofloxacin administration was dropped since the clinical evaluability rules should only be related to clinical data, not microbiological data.
- The primary efficacy outcome measure in the SAP (section 5.1) was further clarified by adding the rules for non-responder.
- Analyses were added to the SAP (section 5.3) for day 21 even though they weren't listed in the protocol.
- The rule, 'patient previously met criteria for failure', in the protocol for clinical response was modified in the SAP (section 5.3) to 'patient previously met criteria for failure and received rescue antibiotics' to specify the rule more precisely.

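### The Day 21 clinical cure rate depends on antibiotic use after TOC, which the plan does not provide for recording, so the rate has no valid reading as written

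*SAP*

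**What the plan says.** SAP 5.3 lists clinical response, derived by program, at EOT and at "Day 12 (+/- 1 day) (TOC) and Day 21 in the ITT, m-MITT" and the CE and ME populations. The same definitions serve all three time points:

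- Cure: "All pre-therapy signs and symptoms of the index infection had resolved such that no additional antibiotics were required".
- Failure includes "persistence or progression of most or all pre-therapy signs and symptoms or use of additional antibiotics for the current infection".
- An earlier failure carries forward under this rule: "Patient previously met criteria for failure and received rescue antibiotics".

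Protocol 6.3.2 gives the whole of the Day 21 procedure: "Call patient to assess for resolution of uUTI symptoms". The schedules of activities (Appendix 1 in both documents) mark only the telephone contact at Day 21, with no concomitant medication check, questionnaire, adverse event or investigator assessment.

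On medication, Protocol 5.4.1 states: "Any concomitant medication which is administered from Screening through the TOC Visit must be recorded in the patient's source record". SAP 7.4 uses the same end point, and Protocol 8.2 ends routine adverse event collection at TOC. Protocol 13.1 adds: "End of Study in all participating countries is defined as the TOC Visit".

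SAP 8 discloses the addition: "Analyses were added to the SAP (section 5.3) for day 21 even though they weren't listed in the protocol". It names no data source for it.

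**The concern.** The Day 21 outcome has two ingredients, symptoms and antibiotic use. The plan supplies the first through the call. For the second, it supplies data only up to TOC. A woman who needed another antibiotic after TOC and was well again by the call looks the same in the specified data as one who stayed well on three days of ciprofloxacin. Day 21 is the only planned assessment after TOC, so a reader will take its cure rate as evidence that the response lasted. The specified data cannot support that, and the SAP does not say how the program should treat the missing element.

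**Working it through.** The documents give no expected Day 21 rate, so there is no planned figure to reproduce. The check traces each element of the definition to its source and then sizes the gap.

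**Step 1. Needed against collected at Day 21**

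| Element in SAP 5.3 | Source specified for Day 21 |
|---|---|
| Symptoms resolved | Telephone call (Protocol 6.3.2) |
| Additional antibiotics up to TOC | Medication records (Protocol 5.4.1, SAP 7.4) |
| Additional antibiotics after TOC | None specified |
| Earlier failure with rescue antibiotics | TOC data, if the antibiotic was taken by TOC |
| Assessment not done, hence indeterminate | That wording names only EOT and TOC |

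**Step 2. Length of the unrecorded interval.** SAP 6.3 puts TOC at Day 12 ± 1 (Days 11 to 13) and the call at Day 21 ± 3 (Days 18 to 24).

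- Shortest: 18 − 13 = 5 days
- Nominal: 21 − 12 = 9 days
- Longest: 24 − 11 = 13 days

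**Step 3. Who can be misclassified.** Re-treatment up to TOC is recorded, and a failure that received rescue antibiotics by then carries forward. A woman still symptomatic at the call is not a cure. That leaves women who were re-treated after TOC and are symptom-free at the call. They include a woman who met the failure criteria at TOC but started an antibiotic only afterwards: the carry-forward rule needs the rescue antibiotic, and its start falls outside the recording period.

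**Step 4. Two ways to program the missing element.** SAP 6.1 expects 250 enrolled and 50 without a qualifying culture, so the expected m-MITT is 250 − 50 = 200.

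*Reading A: no antibiotic record means no antibiotic.* Each such woman is counted as a cure.

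- Effect per patient in the m-MITT: 1/200 = 0.5 points.
- If Day 21 were tabulated for the 40 women expected to have a non-susceptible organism: 1/40 = 2.5 points per patient.
- Illustration, by assumption only: let r be the proportion re-treated after TOC and s the share of these who are symptom-free at the call. The excess is 100 × r × s points. With r = 2% and s = 50%, it is 1 point (2 of 200). With r = 10% and s = 100%, it is 10 points (20 of 200).

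*Reading B: SAP 6.5 applied literally.* A patient is indeterminate if any datum needed for the outcome is missing, and indeterminates stay in the denominator as failures in the ITT and m-MITT. Post-TOC antibiotic use is needed to establish cure and is not specified for anyone, so every symptom-free woman becomes indeterminate. If no site recorded it, the cure rate is 0/200 = 0%.

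The first reading can only raise the rate relative to the definition, and the second drives it toward zero.

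**The case against.** A reader might infer that re-treated relapses do count as cures and that the Day 21 rate is therefore biased upward. The documents do not say so. Reading A is a likely programming default, but SAP 6.5 points the other way. What is established is that the outcome is undefined for these women, not the direction of the error.

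Other objections have some force:

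- Protocol 5.4.1 also asks about interventions at each visit, and requires antibiotics for the primary infection in the CRF without a separate end date. SAP 6.3 lists Day 21 in its visit table, so one could argue that the inquiry reaches Day 21. Against this, both schedules leave medications blank there and both documents end recording at TOC. The Day 21 CRF page is not among the documents, so what the calls actually captured is unknown.
- The missing questionnaire is not in itself a defect for the cure category, because a call can establish whether symptoms have resolved. At most, the part of the failure definition that turns on most or all symptoms would need item-level answers.
- Failure requires antibiotics for the current infection, and the plan does not say whether an episode arising after resolution at Day 12 is the current infection or a new one. Some women re-treated after TOC may not be failures at all. This stands, and it is a further reason to record why the antibiotic was given.
- A larger error among non-susceptible isolates is a natural guess, but no figure in the documents supports it.
- The endpoint is additional and descriptive, SAP 7.6 plans no hypothesis tests, and the addition is disclosed. This limits the stakes but does not make the rate interpretable.

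**Conclusion.** The point holds in a limited form. The Day 21 definition uses antibiotic use after TOC, the plan does not specify recording it, and no rule says how its absence is classified. Only women re-treated in the 5 to 13 days between TOC and the call, and symptom-free at the call, are indistinguishable from sustained cures. Under one reading each adds 0.5 points in an expected m-MITT of 200. Under the other the cure rate collapses toward 0%. The 1 to 10 point range rests wholly on assumed re-treatment and recovery proportions and is not an estimate.

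A reader might also infer that the main efficacy result is in doubt. It is not: the primary outcome is fixed at Day 12, within the medication recording period, and includes a culture. The conclusion assumes that the CRF follows the protocol and schedules as written. If the Day 21 page did capture antibiotic use, stating that in the SAP would largely resolve the point.

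**What to change.** Which change applies depends on whether Day 21 calls are still being made. The SAP is dated 30 July 2019, some 16 months after Amendment 02 of 27 March 2018, so they may be complete.

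- **Calls continuing:** add to the Day 21 call and its CRF page one question on any antibiotic since Day 12, with name, start date and reason. Extend antibiotic recording in Protocol 5.4.1 to Day 21, mark it in both schedules, and bring SAP 7.4 into line. The cost is a slightly longer call and a protocol amendment with prospective IRB/IEC approval (Protocol 12.1). It does not recover calls already made.
- **Calls complete and antibiotic use not captured:** replace the Day 21 cure/failure derivation in SAP 5.3 with *patient-reported symptom resolution by telephone*, and do not call it clinical cure. This costs SAP wording only, but gives up any claim about freedom from re-treatment.

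In either case, name the Day 21 data source in SAP 5.3 and extend the indeterminate wording to a missed Day 21 call. If the cure/failure derivation is kept, also state how absent post-TOC antibiotic information is classified.
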